## STATISTICAL DESIGN AND POWER

Descriptive statistics and exploratory graphing will be generated for all variables of interest measured at all time points (i.e., baseline, mid-treatment, post-treatment, 3-month follow-ups). Data summaries will be produced both for the combined sample, and separately by treatment condition. Variables will be transformed if necessary using Box-cox power transformation. Baseline characteristics will be compared between treatment conditions using ANOVA (or non-parametric Kruskal Wallis test, as appropriate) for continuous variables and a chi-square test for categorical variables. Key baseline variables that differ by condition will be considered for use as covariates in the analyses described below.

**Primary Aim 1.** To assess feasibility and acceptability, we will use the following benchmarks: (a) recruitment success: enrollment of 60 patients; (b) attrition: retention of >75% of patients through all assessments; (c) study retention: patients attend at least 90% of all treatment groups; (d) satisfaction: patients express high satisfaction with RRT based on feedback questionnaires.

**Primary Aim 2.** To evaluate the effect of each treatment condition on hypothesized targets, we will model the pattern of change in reward response to palatable food, reward response to day-to-day life activities, social isolation, and loneliness separately over time using multilevel models (PROC MIXED in SAS). The first level will model individual participant's score on the relevant target over time with baseline as time 0. At the second level, the individual intercept and slope will be entered as outcomes with treatment condition as a predictor. We will examine each treatment condition separately. The cross-level interaction between time and treatment condition will be used to determine the effect of treatment condition on the pattern of change in the hypothesized targets. Restricted maximum likelihood will be used to estimate model parameters and to test the significance of random effects. Both linear and higher-order time effects will be examined based on model selection criterion such as Akaike Information Criterion (AIC) and Bayesian Information Criterion (BIC). With the fitted multilevel model structure, statistical contrasts will be performed at mid-treatment, post-treatment, and 3-month follow-up.

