**Primary Aim 3.** Analyses will be conducted via linear mixed effects models for longitudinal data, which increase power by fully exploiting the strong correlation in treatment outcomes of interests (i.e., percent binge frequency reduction and percent change in EDE global eating pathology) across time. Patterned covariance matrices as implemented in (PROC MIXED in SAS) and will be used to evaluate between group differences for percent binge reduction and percent change in EDE global eating pathology across the study as a whole, and at each assessment post-baseline. Separate variance components will be used to capture therapist and participant-within-therapist variation. The within-subject covariance matrix will be assumed common across study arms, with an exponential variance function to deal with heteroscedasticity and a continuous-time AR(1) correlation matrix to accommodate residual autocorrelation over the unequal-size time intervals between follow-ups. Outcomes at all four time points will be estimated jointly for maximum statistical efficiency in the presence of intermittent missingness and loss to follow-up. The model will include random effects for subject and time (with higher-order effects if needed to capture nonlinear change), and fixed effects for treatment arm, time by treatment interaction, demographic information, and baseline values of binge frequency and global eating pathology. Time-specific covariate-adjusted contrasts will be used to compare outcome between groups.

**Secondary Aim 1.** We will use the same analytic approach described above for Primary Aim 3 but will test the impact of treatment condition on secondary outcomes including depression, substance abuse, and quality of

life.

**Attrition.** Patterns of missing data will be examined. Likelihood-based estimation methods and multiple imputation models will be used to handle missing data. In addition, we will use Hedeker and Gibbons' procedure to examine if dropouts influence the multilevel model results. If the missingness mechanism is related to the missing outcome itself, we will use sensitivity analyses to explore how robust our findings are with respect to a range of assumptions regarding missing data.

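### Secondary Aim 1 names no own-baseline covariate and no outcome form, so its between-arm contrasts may lose precision that scores already collected at baseline could supply

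*SAP*

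**What the plan says.** Secondary Aim 1 in the SAP is a single sentence. It begins "We will use the same analytic approach described above for Primary Aim 3" and applies that approach to the secondary outcomes, which it lists as depression, substance abuse and quality of life. It has no covariate list and does not define the form of the outcomes. Protocol D.6.3 gives the instruments (Beck Depression Inventory-II, ASSIST, Quality of Life Inventory), and D.6 schedules assessments at baseline, mid-treatment, post-treatment and 3-month follow-up.

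The borrowed Primary Aim 3 model is written for "percent binge frequency reduction and percent change in EDE global eating pathology". Besides treatment arm, its fixed effects are "time by treatment interaction, demographic information, and baseline values of binge frequency and global eating pathology". It also has random effects for subject and time. On the responses it says: "Outcomes at all four time points will be estimated jointly for maximum statistical efficiency". The opening paragraph of the SAP lists the time points as "baseline, mid-treatment, post-treatment, 3-month follow-ups", so baseline is one of the four. On the comparison it says: "Time-specific covariate-adjusted contrasts will be used to compare outcome between groups".

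The opening paragraph adds that key baseline variables found to differ between conditions will be considered as covariates.

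**The concern.** Carried over as written, the covariates for a depression score are baseline binge frequency and baseline EDE global, and baseline depression is not among them. The same holds for substance use and quality of life. A patient's own earlier score is usually the best single predictor of a later score on the same scale. Leaving it out lets chance baseline differences pass into the arm contrast and leaves that contrast less precise. With 30 patients per arm, and a SAP that expects to interpret effect sizes where tests are underpowered, the precision of those effect sizes matters.

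The outcome form is a second open point. If the percent-change form of Primary Aim 3 also carried over, a patient with a baseline score of zero would have no defined value. Eligibility (Protocol D.1) requires bulimia nervosa or binge eating disorder, not substance use, so zero scores on the substance-use measure are plausible.

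**Working it through.** **The plan's own figure.** The SAP's Power analyses paragraph gives 154 patients for 80% power, a medium effect, a significance level of 0.05, four assessments and a variance ratio of one. Taking d = 0.5, a two-sided test and equally spaced visits, the squared time deviations sum to 5. Slope reliability is 1/(1 + 1/5) = 0.833. The noncentrality at N = 154 is √(154 × 0.25 × 0.833 / 4) = 2.83, which gives power 0.804, and 154 is the smallest even N that reaches 80%. At N = 60 the same formula gives a detectable d of 0.81, in line with the SAP's statement that it can detect only large effects. The SAP gives no such figure for the secondary outcomes.

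**Inputs for the secondary outcomes.** There are 30 patients per arm (Protocol A.7), or about 23 per arm at the SAP's 75% retention benchmark (0.75 × 30 = 22.5). Two correlations are needed and the documents give neither, so both are assumed:
- ρ, between an outcome's own baseline and its follow-up score: 0.3 to 0.8.
- r, between the inherited baseline covariates (binge frequency and EDE global) and the secondary outcome: 0.2 to 0.4.

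**Does baseline as a response already do the job?** Generalised least squares was applied to four responses with free visit means in each arm, so that the arms may differ at baseline. Variances are relative to the unadjusted difference at one follow-up visit.
- Time-specific arm contrast: 1.00 at every ρ. Having baseline in the response vector does not sharpen it.
- Change-from-baseline (arm-by-time) contrast: 2(1 − ρ) = 1.40, 1.00, 0.60, 0.40 at ρ = 0.3, 0.5, 0.7, 0.8.
- Common baseline mean across arms, or own-baseline covariate: 1 − ρ² = 0.91, 0.75, 0.51, 0.36.

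Own-baseline adjustment therefore also improves on the change contrast. The ratio is (1 − ρ²)/[2(1 − ρ)] = (1 + ρ)/2 = 0.65, 0.75, 0.85, 0.90, which is 35%, 25%, 15% and 10% less variance. The check leaves visit means unconstrained. A straight-line time effect would borrow across visits through its assumed shape, and that was not sized.

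**Against the covariates the SAP does name.** The inherited covariates alone give 1 − r² = 0.96 (r = 0.2) or 0.84 (r = 0.4).

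| ρ | Own baseline, 1 − ρ² | Ratio to 0.96 | Ratio to 0.84 |
|---|---|---|---|
| 0.3 | 0.91 | 0.95 | 1.08 |
| 0.4 | 0.84 | 0.88 | 1.00 |
| 0.5 | 0.75 | 0.78 | 0.89 |
| 0.7 | 0.51 | 0.53 | 0.61 |
| 0.8 | 0.36 | 0.38 | 0.43 |

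Equivalent patients are 60 divided by the ratio. At ρ = 0.5 this is 60/0.781 = 77 or 60/0.893 = 67. At ρ = 0.7 it is 60/0.531 = 113 or 60/0.607 = 99.

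**Detectable d at 80% power**

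| Per arm | Inherited covariates (r = 0.2 / 0.4) | Own baseline (ρ = 0.5 / 0.7) |
|---|---|---|
| 30 | 0.72 / 0.67 | 0.64 / 0.53 |
| 23 | 0.83 / 0.77 | 0.73 / 0.60 |

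These ratios set own baseline alone against the inherited covariates alone. If both are kept, residual variance cannot exceed the smaller of the two, apart from a small loss of degrees of freedom. The 1.08 at ρ = 0.3 with r = 0.4 thus arises from replacing the inherited covariates, not from adding to them.

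**Percent change.** If this form were used, the baseline value would be zero for every patient by construction. Baseline as a response would then carry no information, and the raw baseline score would enter only as a denominator.

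**The case against.** A reader might infer that the secondary analyses never use own baseline. The documents do not support that. Baseline is one of four jointly modelled responses, so the arm-by-time term is referenced to baseline, and a percent change would use baseline as its denominator. The cross-reference can also be read as putting each outcome's own baseline in the place that binge frequency and EDE global hold in Primary Aim 3. Nothing in the sentence excludes this. Chance imbalance is partly covered by the option to consider baseline variables that differ.

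Much of this stands. The text under-specifies the model and does not prove an exclusion. Two parts do not answer the point. The contrasts the SAP names are time-specific, and with a free arm effect baseline as a response does not sharpen them. The imbalance provision is optional and depends on the observed data, whereas adjustment for a prognostic baseline score gains precision whether or not the arms differ.

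A reader might also compute 60/(1 − ρ²) and quote 66, 80 or 118 equivalent patients at ρ = 0.3, 0.5 or 0.7. That compares with no adjustment at all, which is not the planned model. Nor does the SAP say that secondary outcomes are percent changes: it names that form only for binge frequency and EDE global, so the zero-baseline problem is conditional.

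Finally, the stakes are modest. These are secondary outcomes in a randomised pilot that already acknowledges low power.

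**Conclusion.** The concern holds as a gap in specification with a likely cost in precision. No sentence makes baseline depression, substance use or quality of life a covariate, or states the outcome form, and the response structure does not supply the missing precision for the contrasts the SAP names. With ρ from 0.5 to 0.7 and r from 0.2 to 0.4, own-baseline adjustment has about 11% to 47% less variance than the inherited covariates alone, like about 67 to 113 patients instead of 60. These correlations are assumptions. Primary Aim 3 justifies its model by strong correlation of outcomes over time, and if that extends to the secondary measures the upper part of the range is the relevant one. At low ρ the gain is small: with r = 0.4 it is nil at ρ = 0.4, and replacing the inherited covariates would lose precision at ρ = 0.3. Dropping binge frequency and EDE global is therefore not warranted. Randomisation protects the comparison from bias. What is at issue is precision and chance imbalance.

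**What to change.** Amend Secondary Aim 1 to state, for each secondary outcome:

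- The response is the raw score, not percent change.
- Own baseline is used in one of two ways, but not both for the same outcome: (a) as a covariate, with its interaction with visit, in a model of the three post-baseline responses; or (b) as the first of four responses, with a common baseline mean across arms.
- Baseline binge frequency and EDE global may stay as covariates.

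Option (b) keeps the SAP's four-time-point structure and gives the same precision as (a) in the check above. The change takes a sentence or two in the SAP, needs no new data because baseline assessments are already scheduled, and removes an analyst's choice after the data are seen.
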